2.1.8.1 The vaccine

DNA-C CN54ENV

The DNA vaccine will utilize the pVRC8400 plasmid expression vector containing the optimized pCMVR promotor [53] encoding a codon-optimized sequence for clade C gp140. The sequence was derived from a Chinese viral isolate, 97CN54. The C-clade HIV subtype is believed to cause more than 50% of worldwide HIV-1 infections, and is predominant in southern and eastern Africa and India [54]. Previous clinical studies using this plasmid backbone to express similar HIV-1 Env sequences generated low but detectable antibody responses to HIV-1 Env and achieved 70% seroconversion [32] following intramuscular injection without EP. Transgene codon optimization for CN54gp140 and insertion into the pVRC8400 vector have been performed by GeneArt and GMP product has been manufactured by Althea Technology, Inc (USA). There are no specific nonclinical pharmacology studies with the DNA-C CN54ENV vaccine alone. A murine study carried out to inform the design UKHVC_003 trial included a group which received the CN54ENV DNA alone. Whilst a relatively much higher concentration of DNA was used, the DNA was well tolerated and was clearly serving to prime and influence immune responses to the other boosting vaccines used. The env encoding plasmid vaccine (CN54ENV) is very similar in structure and HIV insert sequence to the equivalent plasmid previously tested, in combination with a NYVAC-C boost, in clinical trials EV02 and EV03 [55, 56]. In these studies, priming with DNA at a dose of 4mg on two or three occasions was shown to be well-tolerated and effective in contributing to overall immunogenicity. Identical CN54ENV DNA plasmid is currently in use in the UKHVC spoke 3 (EUDRACT 2012-003277-26) trial initiated in July 2013, which is exploring priming with DNA followed by boosting with MVA combined with CN54gp140 or the same immunogens given sequentially.

CN54gp140

The CN54gp140 is a recombinant gp140 derived from the HIV-1 97CN54 coding sequence and will be manufactured by Polymun, Austria. CN54rGP140, is a trimeric recombinant C-clade envelope protein. The protein comprises a sequence of 670 amino acids, and has been shown to be immunogenic in humans. To date Mucovac 2 (EUDRACT 2010-019103-27) is the only completed trial to have generated safety data on the systemic administration of the CN54gp140 in GLA-AF in healthy volunteers. 100 μ g of protein was administered IM after bedside mixing with GLA-AF (an aqueous formulation of synthetic MPLA). Analysis of the (presumed) peak antibody responses measured after the last immunisation demonstrated induction of robust antibody responses, with moderate neutralization activity against easy to neutralize tier 1 viral isolates.

Preclinical Studies

A Single Dose Biodistribution Study (No 525574) of CN54ENV DNA delivered intramuscularly with electroporation has been performed in rats. The results from this study show that biodistribution of the plasmid is restricted to the site of administration and that there is no persistence of the plasmid in these tissues beyond 60 days. A good laboratory practice (GLP) rabbit tolerance and toxicity study (CR 525569) has been performed to directly support this study, where animals received vaccinations with a 2mg dose of CN54DNA given intramuscularly three times at 3 weekly intervals with electroporation, followed by intradermal or intramuscular boosting with CN54gp140 (100 μ g). There were no adverse

clinical signs that were considered to be related to treatment with DNA-C-CN54ENV, DNA-C-ZM96GPN or CN54 gp140. There was transient very slight local irritation noted after intradermal injection of CN54gp140. There were no worrying local side effects or indications of systemic toxicity. Analysis of the (presumed) peak antibody responses measured 2 weeks after the last immunisation corroborated what had been seen previously in mouse and rabbit studies.

Clinical Studies

In the TaMoVac 1 trial which was carried out in two sites in Tanzania, 40 subjects who had previously been given three doses of HIVIS-DNA followed by two with MVA-CMDR were given two further boosts with 100 μ g CN54gp140, adjuvanted with 5 μ g GLA-AF. The rationale for boosting with CN54gp140 in TaMoVac 1 was informed by the results of RV144 and other trials using recombinant protein vaccines and a desire to complement the T-cell response with a strong B-cell response to HIV envelope. The adjuvanted protein was well tolerated and systemic CN54gp140-specific antibody responses significantly boosted in those primed with DNA and MVA to levels in the range seen in the RV144 trial ([name] personal communication). The neutralising antibody responses were, however disappointing ([name] personal communication) CN54gp140 has also been given to human subjects in two completed trials: MUCOVAC 1 and MUCOVAC 2 and is part of the regimen in 3 ongoing trials: UKHVC-003 which is a two centre Phase I trial running in the UK; TaMoVac 02, a two centre Phase II trial which is running in two sites in Tanzania and one in Mozambique; and X001 which is a single centre trial in the UK.

In MUCOVAC 1, which was conducted in the UK in 2008, CN54gp140 formulated without adjuvant was administered to healthy female volunteers by the IVAG route. Subjects received nine doses over a 3-week period over the course of one menstrual cycle. The vaccine was well tolerated and there were no serious adverse events. The immune responses were disappointing and there were no specific antibody responses detected. One possible explanation given was that the vaccinations were given too close together for optimal priming but there was no adjuvant included in the formulation which may also have contributed [57].

MUCOVAC 2 (EudraCT 2010-019103-27) built directly on MUCOVAC 1 with a continued focus on mucosal immune responses. The trial was conducted in 36 healthy women in two centres in the UK who were randomised to one of four groups to receive CN54gp140 with or without GLA-AF/Chitosan and by a variety of methods. The first (reference) group received three doses of 100 μ g CN54gp10 adjuvanted with 5 μ g GLA-AF (IM high dose), the second received three doses at a lower dose of 20 μ g also adjuvanted with GLA-AF (IM low dose). A third group received a single priming dose of 100 μ g CN54gp140/GLA-AF IM followed by two doses of 500 μ g given intra-vaginally formulated in carbopol gel (IM IVAG) and a fourth received three doses of 100 μ g intranasally formulated in chitosan (IN). Following a protocol amendment, a group of 8 individuals (5 from the high dose IM group and 3 from the IN group) went on to receive 2 further systemic immunisations with GLA-AF adjuvanted CN54gp140 IM. The lower dose (20 μ g) of CN54gp140 was as potent as the higher dose (100 μ g) when given IM with GLA-AF- eliciting systemic binding IgG responses in the majority of individuals in both groups (9/11 and 9/9 respectively). 4/11 and 4/9 of the same women also had cervico-vaginal IgG responses. By contrast, there were no mucosal immune responses detected in the groups of women who received mucosal immunisations (IN or IVAG). Only 1/11 and 0/5 women in the IM IVAG or IN groups made systemic IgG. Interestingly after a single IM boost of the IN group this increased to 3/3, suggestive of amnestic responses and some effect of priming via the IN route. There were

no vaccine related serious adverse events although participants experienced at least one mild or moderate solicited adverse event but there were no safety concerns of note attributable to the study products and all participants completed all their allocated immunisations.

Studies directly supporting the design of CUTHIVAC002

Preclinical studies

To directly support the design of this trial Mann and colleagues carried out studies in mice and rabbits using a similar DNA plasmid encoding env for priming and the same CN54gp140 protein for boosting. The aims of the studies were (i) to assess the impact of DNA priming via different methods on T-cell and B-cell responses and (ii) to assess the impact of EP on each route after boosting with CN54gp140 [41]. The first part of the murine study was focussed on the optimisation of DNA priming. Vaccine specific antibody and cellular responses could be seen after DNA priming alone, which is one advantage of the model. Results showed that priming via the ID route favoured T-cell responses whilst the IM route favoured B-cell responses and that both were significantly augmented by EP. They also clearly showed that in addition to increasing the magnitude of the antibody response to CN54gp140, when given with both ID and IM priming , EP also increased the avidity of the antibody response. The greatest impact upon the avidity of the response was seen only when EP was given with both ID and IM priming suggesting that both the T-cell and B-cell responses were required for optimal avidity.

The same study also examined the optimal route for boosting with CN54gp140 DNA priming ID/IM with or without EP. The effect of DNA priming was striking and antibody responses were generally poor without it. Of the methods tested, subcutaneous (SC) and intranasal (IN) boosting was the best for generating systemic IgG responses, with IM boosting performing almost as well. IN boosting was significantly better than any other method in terms of IgA responses followed by the SC and IM methods. The transcutaneous route (TC) was able to boost systemic antibody responses but IgA responses were disappointing. In contrast to what was seen for antibody responses, the route of boosting with CN54gp140 did not have much impact on the magnitude of cellular responses seen after DNA priming (ID and IM) in the absence of EP but without priming, the responses were negligible. Studies in rabbits also clearly showed that priming by combined ID and IM immunization delivered with electroporation, followed by boosting SC resulted in antibody responses with neutralising activity (Tier 1) and that both were required for optimal responses. Increasing antibody affinity could also be seen after repeated protein boosts. Additional animal studies have shown that the route of DNA administration (IM vs. ID) can also impact on the quality of antibody induction. Recent studies in macaques suggest that both ID/EP and IM/EP DNA delivery promoted robust antibody responses to SIV Envs (reciprocal endpoint titre log 4.5–5) but that ID/EP administration induced higher cross-reactive neutralizing responses than IM/EP administration [58].This is further supported by previous studies using DNA encoding H5 hemagglutinin where concomitant IM/EP plus ID/EP induced significantly stronger responses than either route individually [59].These data suggest that split dose vaccination when given at different anatomical sites may have a positive impact on the magnitude of induced antibody responses. While these preclinical data are promising, differences in skin structure and resident immune cell populations between species mean the relative merits of ID/EP and IM/EP in the context of Env DNA can only be accurately determined in humans. Therefore we will also assess the impact of concurrent ID and IM administration in this study.

Clinical studies: CUT*HIVAC_001

This Phase I trial, which is fully recruited and volunteers are currently in follow up in London, is part of the same programme of research and is also exploring different methods of vaccination with a similar HIV DNA plasmid vaccine developed by FitBiotech and encoding a polypeptide containing peptides derived from envelope and core proteins.

The primary objective of this study is the induction of CD8 T cell responses to the vaccine immunogen. 30 healthy volunteers were randomised to receive 13.2 mg of GTU® MultiHIV B clade DNA plasmid given in three immunisations over 12 weeks via (i) IM and ID (ii) IM and Transcutaneously (TC) or (iii) IM with EP (Ichor TriGrid device). The transcutaneous route has been shown to favour the development of CD8+ T-cell responses in animal models and also in one Phase I clinical trial of a licensed influenza vaccine.

2.2 Rationale and Objective

2.2.1 Study Rationale

We will explore three combination regimens with and without EP with the overall aim of (i) optimising humoral and cellular immune responses (ii) developing safe and well tolerated vaccination strategies. We propose to combine the previously used IM and ID methods because clinical and preclinical data suggest that the combination will favour the development of balanced immune responses. All groups will receive 3 doses of 2.0mg of the CN54ENV plasmid DNA (CN54ENV) vaccine in 0.5ml volume IM together with 3 doses of 0.6mg of the CN54ENV vaccine in 0.15ml ID each given at 4 weekly intervals over 8 weeks followed by 1 dose of 50 μ g CN54gp140 ID at Week 20. A directly supportive murine study using a similar DNA vaccine, the same CN54gp140 protein and following the same design (albeit using a different EP device) demonstrated that priming via the combined IM+ID route favoured the development of high avidity humoral immune responses. This is further supported by the preclinical toxicology study (CR 525569) performed in rabbits using one of the Ichor devices that will be used in this study.

We are interested to see whether such concomitant priming performs similarly well in man resulting in optimal balanced immune responses. DNA vaccines have been relatively disappointing in man but there is still great interest in this platform because of its intrinsic flexibility, the relatively low cost of production of GMP material and the speed at which immunogens can be modified. We will be able to assess the effect of EP on each different route of vaccination and also to make a direct assessment of the translation of the very clear results seen in the murine study to the human which would be of general benefit to the field [34]. The trial is not powered to carry out formal statistical comparisons between the three groups and the immunological component is intended to be primarily descriptive.

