10.4.2 Immunogenicity

10.4.2.1 Primary Immunogenicity Outcomes

All serum samples will be screened for antigen specific antibodies IgG (and IgA). The absolute levels of antibody in samples that are found to be positive will be determined using a standardised and quantitative ELISA developed in [name]'s laboratory at Imperial College London. In this sandwich capture ELISA, the Ab of interest is captured by the relevant target antigen and then detected using a labelled isotype specific secondary Ab. An estimate of the concentration of Ab in the sample is calculated by interpolation relative to a standard curve based on titration of purified human standards IgG or IgA captured by anti-human kappa/lambda-specific antibodies. The number of 'responders' in each assay will be presented by time-point and group as a proportion with 95% confidence interval. A 'responder' will be defined as a participant in whom a response was detected in at least one post treatment immunogenicity sample. Titres of antigen specific antibodies will be described by time-point and group, and compared using rank tests where appropriate. Although all samples will be processed, the analyses will be for the per-protocol population and conducted in [name]'s laboratory.

10.4.3

Exploratory Immunogenicity Outcomes

The proportion of individuals mounting a B cell response using frozen PBMC will be determined by B cell Elispot assay for antigen induced IgG production from antibody secreting cells (ASC's). CN54gp140 specific responses will be analysed as well as total IgG and compared between vaccine groups.

In addition vaccine induced T cell responses will be analysed by T cell Elispot assay for IFN- γ production on frozen PBMC samples and the proportion of individuals mounting a response quantified as SFU (spot forming units) compared between vaccine groups. These exploratory analyses will use descriptive statistics and will be conducted in [name]'s laboratory.

10.4.4

Safety Outcomes

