2.1. Randomisation

Participants will be block-randomised using a computer-generated algorithm with a back-up manual procedure and randomisation will be stratified on the basis of gender. The randomisation lists are generated and checked by the trial statistician, and stored securely in the trial database.

Participants are randomised 1:1:1 to ID/EP, IM/EP or ID/IM/EP. Randomisation is unblinded.

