3.3. Exploratory Endpoints

3.3.1. Immunogenicity

- Frequency and magnitude of HIV-gp140 specific B-cell-mediated responses in the systemic compartment measured by B-cell ELISPOT
- The magnitude of vaccine specific systemic T cell responses by T cell ELISpot assay
- The magnitude of antigen specific systemic IgA antibody responses ($\mu\text{g/ml}$)
- Frequency, titre and avidity of serum binding antibodies to other HIV Env antigens (alternative clades) by ELISA or other assays.
- Mapping of serum binding antibodies using Env subunit constructs (e.g., V2 scaffolds and hotspots) by ELISA.
- Frequency and magnitude of mucosal IgG and IgA antibody responses to CN54gp140 measured four weeks after the final immunisation.
- Frequency and titre of serum neutralising antibodies to homologous virus, and, if warranted a wider panel of viruses representing different clades.
- Frequency and magnitude of HIV-specific T-cell mediated responses measured by T-cell CFSE, and ICS (Intracellular Cytokine Staining).
- Frequency and magnitude of T-cell chemokine and cytokine release following ex-vivo antigen stimulation quantified by Luminex.
- Isolation and characterization of Env-specific monoclonal antibodies (IgG) from memory B cells in the systemic compartments (dependent upon elicited specific memory B-cell numbers).
- Characterisation of non-neutralising antibody function using ADCC/ADCVI, viral capture and aggregation assays.
- Epitope mapping of B- and T-cell responses.

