4.7. Exploratory Analysis

Proportions and their 95% CIs will be reported for the categorical exploratory outcomes defined in 3.3, with arms compared using Fisher's exact test. For continuous outcomes means or medians will be presented as appropriate, and arms compared using Welch tests.

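### SAP 4.7 tests exploratory immunogenicity outcomes between arms, where the protocol's ELISpot plan is descriptive, and sets no error rule and gives no between-arm estimate

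*Protocol*

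**What the plan says.** Protocol 2.2.1 states that the trial lacks power for "formal statistical comparisons between the three groups and the immunological component is intended to be primarily descriptive". Protocol 10.3 and SAP 2.2 both disclaim statistical confidence about group differences.

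Protocol 10.4 says the SAP will be built on the summary that follows it. In that summary, 10.4.3 covers the B-cell and T-cell ELISpot assays. It says results will be compared between vaccine groups and then gives the method: "These exploratory analyses will use descriptive statistics".

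SAP 4.7 gives a different method. Proportions and 95% intervals are reported "for the categorical exploratory outcomes defined in 3.3, with arms compared using Fisher's exact test". It continues: "For continuous outcomes means or medians will be presented as appropriate, and arms compared using Welch tests". SAP 3.3.1 lists 12 immunogenicity items, several with two components, for example "Frequency and magnitude of HIV-gp140 specific B-cell-mediated responses in the systemic compartment measured by B-cell ELISPOT". SAP 3.3.2 adds pain scores.

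**The concern.** For the two ELISpot assays the documents give different instructions for the same data. For the other exploratory immunogenicity outcomes, protocol section 10 names almost no method, so SAP 4.7 alone introduces the testing, against the general statement in 2.2.1.

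The tests come without what a reader needs to interpret them. SAP 4.7 gives no significance level, no multiplicity rule, no general time-point and no statement that the p-values are exploratory. Proportions get per-arm Wilson intervals (SAP section 4 and Table 3). Continuous outcomes get no interval, and neither type gets a between-arm estimate. Medians may be reported beside a Welch test, which compares means.

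Two misreadings could follow. Some small p-values would be expected by chance and could be taken as effects of delivery method. With 8 per arm, large p-values would say little, and no interval would show how little.

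**Working it through.** **Inputs.** Three arms at 1:1:1 (SAP 2.1), so 3 pairs per outcome. Eight per arm (protocol 10.3, SAP 2.2). Twelve immunogenicity items (SAP 3.3.1), taken at one time-point each. Assumed, because 4.7 states neither: pairwise tests, and two-sided 0.05 without adjustment. Pairwise testing is stated only for safety (SAP 4.5.1, carried into 4.6.1).

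**The plan's own figures.** Neither document gives an error rate or power for these tests. The nearest figures are the Wilson intervals in SAP Table 3, which reproduce for n=8: 0/8 gives 0-32%, 4/8 gives 22-78%.

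**Nominal benchmark, independent tests.**
- 12 × 3 = 36 tests: 1 − 0.95^36 = 0.84.
- One test per outcome, 12 tests: 1 − 0.95^12 = 0.46.

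The 36-test figure is too high, because pairs share arms and the real test sizes at n=8 are below 5%.

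**Welch tests at 8 per arm, simulated with no true effect.** The size per pair is 0.048 for normal data and 0.024 for lognormal data (log-SD 1). The chance that any of 3 pairs gives p<0.05 is 0.117 and 0.064. For 12 independent endpoints:
- normal: 1 − (1 − 0.117)^12 = 0.78;
- lognormal: 1 − (1 − 0.064)^12 = 0.55.

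With the 12 endpoints equally correlated (simulated, accurate to about one percentage point):

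| Correlation | Normal | Lognormal |
|---|---|---|
| 0 | 78% | 55% |
| 0.6 | 55% | 41% |
| 0.9 | 30% | 23% |

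The expected number of false positives does not depend on correlation: 36 × 0.048 ≈ 1.7 for normal data and 36 × 0.024 ≈ 0.9 for lognormal.

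**Fisher tests at 8 v 8, exact.** The size per pair is at most 0.021, and at most 0.056 for any of 3 pairs, both at a true response rate of 0.5. For 12 independent endpoints:
- rate 0.5: 1 − (1 − 0.056)^12 = 0.50;
- rate 0.2: 1 − (1 − 0.0112)^12 = 0.13;
- rate 0.1: 1 − (1 − 0.0009)^12 = 0.01.

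**The other direction.** A two-sided t-test at 8 v 8 has 46% power for a true difference of 1 SD and about 80% at 1.5 SD. Response rates of 0/8 v 4/8 give Fisher p=0.077.

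**The case against.** The strongest reply is that the protocol does not rule out testing in the immunology. Section 2.2.1 says *primarily* descriptive. Section 10.4.2.1 plans it for titres: "Titres of antigen specific antibodies will be described by time-point and group, and compared using rank tests where appropriate". Section 2.2.4 poses a hypothesis of significantly greater antibody responses in group 3. This stands. A reader might infer that the protocol bars all between-group tests, or that 10.4.3 makes all 12 endpoints descriptive; neither holds. The descriptive-statistics sentence directly covers the two ELISpot assays only.

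A reader might also infer that later decisions on delivery method hang on these p-values. They do not: the explicit rules in 2.2.4 rest on solicited events of grade 3 or above, discontinuations, and the proportion making systemic IgG. What remains is that 2.2.4 also lists broader hypotheses, such as balanced immune responses, to inform future trials, and exploratory assays bear on those.

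SAP section 4 says immunogenicity data are analysed outside the trials unit, and the SAP has no shell table for them. So 4.7 may not be what the laboratory follows. That lessens the practical risk but leaves the laboratory with two conflicting instructions.

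Finally, three pairwise intervals per endpoint do not remove multiplicity. This stands too, and intervals can be less conservative than Fisher's test. For 0/8 v 4/8, the Newcombe lower limit is 0.50 − √(0.285² + 0.324²) = 0.07 and the upper limit is 0.50 + 0.285 = 0.78, which excludes zero although Fisher gives p=0.077. The gain is that the size and uncertainty of a difference become visible; the label against significance claims is essential.

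**Conclusion.** The point holds as a minor inconsistency. SAP 4.7 departs from protocol 10.4.3 for the ELISpot assays. It also extends significance tests to the remaining exploratory immunogenicity outcomes without an error rule or a between-arm estimate.

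The chance of at least one spurious p<0.05 could exceed three in four, but only with 12 independent, normal, continuous endpoints tested pairwise at 0.05. It falls to 23-30% at correlation 0.9 and can be very low for Fisher tests at low response rates. A reader might infer that false positives are likely whatever the data look like; the documents do not support that. Some items, such as epitope mapping and antibody isolation, may yield nothing testable, which lowers the figures. Items with both frequency and magnitude, and repeated sampling (protocol 7.1 lists nine post-enrolment serum times, the week 44 visit being for known responders only), would raise them. The mucosal endpoint already has its own time-point.

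Nor is it right that no intervals are planned: per-arm intervals for proportions are. The primary IgG analysis is untouched.

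**What to change.** In SAP 4.7, replace the Fisher and Welch tests for exploratory immunogenicity with:
- by-arm summaries;
- between-arm differences with 95% intervals for groups 3 v 1, 3 v 2 and 1 v 2: Newcombe for proportions, and the log or rank scale for continuous outcomes;
- one named time-point per assay;
- a sentence saying that these intervals are exploratory, are not adjusted for multiplicity and support no claim of significance.

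If the tests are kept, amend protocol 10.4.3 to match. State in 4.7 the level, which pairs are tested, and that the p-values are unadjusted and exploratory.

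The first option changes only SAP wording. It gives up p-values for exploratory outcomes, which protocol 10.4.3 does not promise. The second also needs a protocol amendment.
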